A Randomized Trial of Transcutaneous Nerve Stimulation for Overactive Bladder Patients

[name]

Assistant Professor, Western University

NCT 02511717

March 1 2016

Statement of Objective

To determine the efficacy of transcutaneous tibial nerve stimulation (using skin patch electrodes) for the treatment of women with clinical symptoms of overactive bladder.

Background

Overactive bladder is a clinical diagnosis characterized by “urinary urgency, often with frequency and nocturia, with or without urgency urinary incontinence”². Approximately 16% of adult women meet the clinical definition for overactive bladder, and approximately 1/3 of them will have urgency incontinence^{3,4}. While a small proportion of patients do see their symptoms resolve after a year, for the vast majority this is a chronic condition^{4,5}. Although it is not inherently dangerous, overactive bladder is an important condition given its wide-ranging impact on overall quality of life and mental health³. The magnitude of impact across different domains of quality of life is similar to chronic diseases such as diabetes⁶. In addition, the financial impact is substantial; in the United States this has been estimated at \$12 billion annually⁷.

Hypothesis

I hypothesize that the study protocol of transcutaneous tibial nerve stimulation performed at home during 30 minute sessions, 3x/week, for 12 weeks will be associated with a statistically significant improvement in overall bladder symptoms.

Design and methodology

Study design: This is a randomized, double blind, sham controlled clinical trial. The primary intervention is 30 minute sessions, 3x/week, for 12 weeks of transcutaneous tibial nerve stimulation sessions carried out at home. The sham intervention will consist of the same treatment schedule, except with the application of transcutaneous nerve stimulation to the lateral aspect of the lower leg, away from the tibial nerve. Patients will undergo a 12 week treatment course. The patient and the treating physician will be blinded to the group assignment of the patient. Randomization will be done using a random number generator, and study assignment will only be released at the end of the study. Only the study nurse instructing the patient on placement of the study electrodes will know the patient assignment. The effectiveness of our sham protocol will be evaluated with a question during week 2-3 asking if they think they are in the active or sham group. The study visit schedule is outlined in more detail in Appendix 2.

Inclusion criteria

1. Female, >18 years of age, with the clinical diagnosis of overactive bladder (based on the current ICS definition²).
2. Failure of behavioral measures and pharmacologic therapy to adequately control overactive bladder symptoms.
3. Baseline patient perception of bladder condition score of 2 or higher.

Exclusion criteria

1. Current or previous percutaneous or sacral neuromodulation therapy
2. Stress predominant urinary incontinence

3. Newly added bladder medication or dose change with the last 2 months (Tamsulosin, Silodosin, Alfuzosin, Terazosin, Baclofen, Diazepam, amitriptyline, imipramine, DDAVP, tolterodine, oxybutynin, fesoterodine, darifenacin, solifenacin, trospium, mirabegron)
4. Intravesical botulinum toxin use within the last 1 year
5. Implanted pacemaker or defibrillator
6. History of epilepsy
7. Unable or unwilling to commit to study treatment schedule
8. Pregnant, or possible pregnancy planned for the duration of the study period
9. Active skin disease of the lower legs (dermatitis, cellulitis, eczema, trauma)
10. Documented allergy to patch electrodes or their adhesive
11. Abnormal sensory function of the lower limb
12. Metallic implant within the lower limb

Intervention: Transcutaneous electrical nerve stimulation is a safe and effective therapy that has been used by physicians and other health professionals for a variety of conditions such as pain and muscle rehabilitation^{26,27}. We will use the EV-906 Digital TENS machine (from Everyway Medical Instruments Co Ltd, Health Canada License #73631). Two adhesive patch electrodes will be applied to one of the patient's lower limb, and the location used will be based on their treatment assignment (active treatment versus sham). The initial treatment will be carried out in the clinic under the supervision of the investigating physician, with training provided for the patient on proper use of the device by the study nurse. The remaining treatments will be detailed on a calendar for the patient, with telephone contact every 2-3 weeks with research staff to assess compliance. When undergoing active treatment, patients will have the electrodes applied posterior to the medial malleolus, and 5-10 cm above the medial malleolus of the same leg, just behind the medial tibial edge. As per previous studies involving transcutaneous posterior tibial nerve stimulation^{25,28,29} and similar to percutaneous tibial nerve stimulation²³, we will use the bipolar stimulation setting, with a frequency of 10 Hz, 200ms pulse, and the amplitude will be titrated up to patient's maximum nonpainful tolerance (between 0.5-10mA). For patients undergoing sham treatment, they will have the patch electrodes placed on the lateral side of the lower limb, and told to keep the current setting stable at 1mA. This will prevent any meaningful stimulation of the tibial nerve, while still delivering a slight tingling sensation to simulate active treatment.

Primary outcome measure: The patient perception of bladder condition (PPBC) is a commonly used measure for global response in overactive bladder studies. It is an ordinal scale from 0-5 (Appendix 3). It is a valid, reliable and responsive single question asking the patient to select the degree of problems associated with their bladder condition³⁰. Patients will be categorized as responders (score improvement by 2 points between screening visit 1 and end of study visit 3) or nonresponders.

Secondary outcome measures:

1. OAB related quality of life (OAB-q SF) Valid, reliable, and responsive tool for assessing symptom bother and OAB related quality of life³¹.

2. 3-day voiding diary parameters (daily voiding frequency, functional bladder capacity, mean voided volume, longest time between voids, nocturia, number of urgency incontinence episodes). This is a valid and reliable measure of urinary symptoms³².
3. Quantification of urinary incontinence with 24hr pad weights. This is stable, reliable and responsive measure of the degree of urinary incontinence^{33,34}.
4. Physician assessment of benefit will be completed based on a standard clinical history at study visit 3 (end of study), and graded on a 7 point global response assessment.

Data Analysis and Sample Size

Analysis of our primary outcome will be an intention to treat analysis (using the chi squared test) based on the proportion of patients classified as a responder using the change in the patient perception of bladder condition. A secondary analysis, based on a per protocol analysis (for efficacy) will be performed for patients who completed at least 80% of the treatment sessions for at least 20 min each (determined from patient completed treatment diary, and electronic usage log in the TENS device). Secondary endpoints will be analyzed as appropriate using the students t-test or chi squared test. All data analysis will be carried out using SAS 9.2.

Using previous percutaneous tibial nerve stimulation studies as a guide²³, we estimate 20% of sham patients and 60% of actively treated patients will be responders. Using the Chi-square test, a two-sided alpha of 0.05, and 80% power, 27 patients per group will be required. Our final sample size, adjusting for a 10% dropout rate, is 60 (30 per group). Our sample size calculation is based on our intention to treat analysis.

References

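### Exclusion 1 omits earlier or current transcutaneous tibial stimulation, the treatment under test, so women who may recognise the sham or still be using the therapy can be randomised

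*Combined protocol and SAP*

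**What the plan says.** The Statement of Objective names the treatment under test: "To determine the efficacy of transcutaneous tibial nerve stimulation (using skin patch electrodes". Exclusion criteria, item 1, bars "Current or previous percutaneous or sacral neuromodulation therapy". The Intervention section keeps the transcutaneous and percutaneous routes apart. It takes its stimulation settings "As per previous studies involving transcutaneous posterior tibial nerve stimulation" and then describes them as similar to those of the percutaneous technique.

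The arms differ in ways the patient can see and feel. In the active arm "patients will have the electrodes applied posterior to the medial malleolus, and 5-10 cm above the medial malleolus of the same leg", and the current is raised to the highest level she tolerates without pain. In the sham arm "they will have the patch electrodes placed on the lateral side of the lower limb, and told to keep the current setting stable at 1mA".

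Under Study design, patient and treating physician are blinded, and one question at week 2-3 asks the patient which group she thinks she is in. The primary outcome is the PPBC, a single self-rated item. A responder improves by 2 points between Visit 1 and Visit 3.

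**The concern.** Item 1 keeps out women with experience of two related forms of neuromodulation and is silent on the form being tested. No reason is given, and it looks like an oversight. Three things are at stake.

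- **Masking.** A woman who was taught the medial ankle placement may recognise a lateral placement with a current she is told not to raise. Her own rating then decides whether she counts as a responder.
- **Baseline.** A woman still benefiting from stimulation at Visit 1 has a lower PPBC score and less room for a 2-point fall. At the entry minimum of 2, only a score of 0 would make her a responder.
- **Contrast.** Item 1 bars current percutaneous or sacral therapy, but nothing stops a current transcutaneous user from continuing with her own device. In the sham arm this would narrow the difference between groups.

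**Working it through.** **1. Does any other text close the gap?** The three inclusion criteria cover sex, age and diagnosis; prior treatment failure; and baseline PPBC. The prior-treatment criterion is "Failure of behavioral measures and pharmacologic therapy to adequately control overactive bladder symptoms", which does not mention stimulation. The other 11 exclusions cover stress-predominant incontinence, recent bladder drug changes, botulinum toxin, cardiac devices, epilepsy, commitment to the schedule, pregnancy, skin disease, electrode allergy, sensory loss and metal implants. None removes a past or current user. Appendix 2 lists a medical history, a criteria review and a medication and health review at Visit 1, but no item on earlier transcutaneous stimulation. The gap is therefore in the current text.

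**2. The plan's own sample size.** Inputs from Data Analysis and Sample Size: 20% sham, 60% active, two-sided alpha 0.05, power 80%, 27 per group, 10% dropout, 30 per group.

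- Uncorrected: n = [1.960·√(2·0.4·0.6) + 0.842·√(0.2·0.8 + 0.6·0.4)]² / 0.4² = 22.3, so 23 per group.
- With continuity correction: n = (22.33/4)·[1 + √(1 + 4/(22.33·0.4))]² = 27.1. The stated 27 is this figure to the nearest whole number; rounding up gives 28.
- Dropout: 27/0.9 = 30 per group, 60 in total.

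The stated figure reproduces, and the eligibility point does not change it.

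**3. Illustration of dilution.** The documents give no share of previously exposed women. Assume a share f, equal in both arms, in whom the technique failed before and who respond at the sham rate whichever arm they are in.

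Active rate = 0.60(1 − f) + 0.20f = 0.60 − 0.40f; the sham rate stays at 0.20.

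- f = 3% (0.03 × 30 = 0.9 women per arm): 0.60 − 0.012 = 58.8%
- f = 10% (0.10 × 30 = 3 women per arm): 0.60 − 0.040 = 56.0%

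Exact power is the sum of the two-binomial probabilities over all outcomes where the chi-squared statistic exceeds 3.84. The plan does not say whether the test is continuity-corrected, so both versions are shown.

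| Active rate (vs 20%) | 27 per group, uncorrected | 27 per group, corrected | 30 per group, uncorrected | 30 per group, corrected |
|---|---|---|---|---|
| 60% (f = 0) | 86.8% | 80.2% | 90.5% | 85.1% |
| 58.8% (f = 3%) | 84.8% | 77.7% | 88.7% | 82.7% |
| 56% (f = 10%) | 79.6% | 71.3% | 83.6% | 76.3% |

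**4. Masking, baseline and own-device use.** These cannot be sized from the documents. Any figure would need both the share exposed and response rates among women who recognise their arm, and neither is given. For scale, one woman changing category moves an arm's rate by 1/30 = 3.3 points.

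**The case against.** The strongest objection is that nothing shows any candidate has had this treatment. A reader might infer from the Intervention section that exposure is common, but it says only that TENS "has been used by physicians and other health professionals for a variety of conditions such as pain and muscle rehabilitation". Neither named use is a bladder condition, and the cited transcutaneous studies show that the technique has been researched, not that women at this site have received it. This stands: prevalence is unknown.

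A reader might also infer that prior non-responders would bias the result, and that the inclusion criteria favour them. Neither follows. Exposure precedes randomisation and is balanced between arms in expectation, so the intention-to-treat comparison stays valid and the cost is dilution and power. The inclusion criterion requires failure of behavioural and drug treatment, so a past responder who stopped and relapsed qualifies just as well.

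It is fair to add that the visible difference between arms is a property of the sham for every participant, and that the plan does check masking. Amending item 1 will not alter the sham. It would keep out the women best placed to recognise it, whereas the week 2-3 question only records a guess after the event. That an exposed woman may recognise her arm is a reasonable inference from the design, not a certainty.

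Finally, on the uncorrected test even the 10% illustration leaves power at 79.6% with 27 per group, close to the planned 80%. That is correct, and it is why the case does not rest on power.

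**Conclusion.** The gap is real and unambiguous: as written, the criteria admit past and current users of the study treatment to a masked sham trial with a self-rated primary outcome. The main threat is to masking. For current users there is also a threat to the Visit 1 baseline and to the separation between arms. The size is unknown and may be zero. The power losses in the table rest wholly on an assumed share of 3% to 10%, all of them prior non-responders responding at the sham rate; they illustrate the effect and do not predict it. The documents do not support a claim of a known direction of bias or of an error in the sample size. This is a cheap improvement worth making, not a defect that invalidates the design.

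**What to change.** Add *transcutaneous tibial* to the therapies listed in exclusion 1, alongside percutaneous and sacral, limited to use *for bladder symptoms* and covering both current and previous use. Place the limiting phrase so that it does not unintentionally narrow the existing bar on percutaneous and sacral therapy. Ask about it in the Visit 1 history.

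A blanket exclusion of any lower-limb TENS would go further than the problem requires, since women using it for unrelated conditions have no bladder response to carry over. Record such use at Visit 1 instead.

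If the sponsor prefers to admit women with earlier transcutaneous tibial stimulation, the protocol should say so, record the exposure at screening, and report the primary result and the masking answers by it.

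The cost is a few words in one criterion and one history question at an existing visit, with no new procedure. The downside is the loss of a few otherwise eligible women.

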Appendix 2. Study schedule.

STUDY SCHEDULE	Visit 1 Screening	Visit 2 Randomization	Telephone Followup	Visit 3 End of study
Visit Windows	1- 4 weeks prior to Randomization	Week 0	Every 2-3 Weeks	12-13 Weeks
Documentation of Consent	X			
Medical History and Physical Exam	X			
Inclusion/ Exclusion Criteria Review	X			
Medication and Health Review	X			X
Urine Pregnancy Test	X			
PPBC Questionnaire	X		X (week 6-7 only)	X
OAB-q SF Questionnaire	X			X
3 day Voiding diary	Diary Provided	Completed diary returned & new one provided for Visit 3		Completed diary returned
24hr Urinary Pad test	Supplies Provided with instruction	Pads Returned & new ones provided for Visit 3	Pad test done 1-7 days prior to visit 3	Pads Returned
Randomization		X		
Initial 30 minute treatment session in clinic with nurse supervision		X		
Assessment of treatment masking			X (week 2-3 only)	
Assessment of compliance, review instructions, address any adverse events or questions			X	
Physician assessment of benefit				X

Appendix 3. Patient perception of bladder condition. Scored 0 (no problems) to 5 (severe problems).

(PPBC)

Which of the following statements describes your bladder condition best at the moment? Please mark “X” in one box only.

My bladder condition does not cause me any problems at all.

My bladder condition causes me some very minor problems.

My bladder condition causes me some minor problems.

My bladder condition causes me (some) moderate problems.

My bladder condition causes me severe problems.

My bladder condition causes me many severe problems.

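### The Intervention section puts a physician, and Appendix 2 a nurse, in charge of a first session where electrode site shows the arm; the physician rating benefit at Visit 3 is not identified

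*Combined protocol and SAP*

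**What the plan says.** The Study design section describes the trial as double blind and sets two rules: "The patient and the treating physician will be blinded to the group assignment of the patient", and "Only the study nurse instructing the patient on placement of the study electrodes will know the patient assignment".

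The Intervention section then describes the first treatment: "The initial treatment will be carried out in the clinic under the supervision of the investigating physician". The rest of that sentence gives device training to the study nurse. The same section makes electrode position depend on the arm ("the location used will be based on their treatment assignment (active treatment versus sham"). For active treatment, "patients will have the electrodes applied posterior to the medial malleolus" and at a second point higher on the inner side of the same leg. For sham, "they will have the patch electrodes placed on the lateral side of the lower limb".

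Appendix 2 lists the same session, at Visit 2, as "Initial 30 minute treatment session in clinic with nurse supervision".

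Item 4 of the secondary outcome measures is a physician's assessment of benefit at Visit 3, graded on a 7-point global response scale from a clinical history. Neither item 4 nor its row in Appendix 2 says which physician does this or what that physician may have seen.

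The only masking check in the plan is put to patients: "The effectiveness of our sham protocol will be evaluated with a question during week 2-3".

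**The concern.** The two descriptions of the first session name different supervisors, and the difference bears on blinding. The arms differ visibly in where the electrodes sit. A physician who supervises in the ordinary sense, present while the electrodes are on, can read the assignment from the leg.

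That would break the rule that only the nurse knows the assignment, whoever rates later. If the same physician also gives the Visit 3 rating, a subjective outcome would be scored by someone who knows the arm, in a trial that would be reported as double blind. The planned masking question would not reveal this, because it asks patients what they believe and asks physicians nothing.

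**Working it through.** No figure in the plan depends on this point, so the check compares the texts and then counts what is exposed.

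**Who is at the first session**

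| Source | Supervisor named | Fits the rule that only the nurse knows the arm? |
|---|---|---|
| Intervention | Investigating physician (nurse trains the patient) | Not if the physician sees the electrodes |
| Appendix 2, Visit 2 | Nurse | Yes |

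Four rows of Appendix 2 have a Visit 2 entry: voiding diary, pad test, randomization and the initial session. One of the four names staff, and it names the nurse. The only row in the whole table that names a physician is the Visit 3 assessment of benefit.

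**Does the session reveal the arm?** Yes, through electrode site: medial in one arm, lateral in the other. Current is a weaker cue and is not relied on here, because the active range of 0.5–10 mA includes the sham setting of 1 mA.

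**Does that reach an outcome?** Three conditions must all hold:

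1. The Intervention wording is followed literally, so the physician attends.
2. The physician sees the electrodes.
3. The same physician rates benefit at Visit 3.

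The documents settle none of these. They do not define supervision. They also do not say whether the investigating physician, the treating physician and the Visit 3 rater are one person. Conditions 1 and 2 are enough to break the rule that only the nurse knows. Condition 3 is needed for the rating itself to be unblinded.

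**How much is exposed**

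- Outcomes: 1 of 4 numbered secondary measures. With the six diary parameters counted singly, the total is 1 (OAB-q SF) + 6 (diary) + 1 (pad weight) + 1 (physician rating) = 9, of which 1 is exposed.
- Patients: up to 60 (30 per group).
- Sessions: 3 per week × 12 weeks = 36 per patient, of which 1 is described as taking place in clinic. This does not scale the risk down, since one sighting is enough to unblind.
- Primary outcome: PPBC is completed by the patient, so it is not directly exposed.

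The documents give no basis for the size or direction of any bias in the rating, so none is calculated.

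**The case against.** The best defence is that the blinding rule is already clear. The Study design section excludes everyone but the nurse from knowing the assignment, which covers any physician who might rate, and it withholds assignments until the study ends. Supervision may mean only medical responsibility while the nurse runs the session. On that reading all the passages agree, and Appendix 2, to which the Study design section refers for detail, supports it. The harm needs three unproven conditions and touches one secondary outcome.

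Much of this stands. Oversight without attendance is a possible reading, unblinding of the rater is a risk and not an established fact, and the reach is limited.

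It does not remove the point. A general rule does not cure a specific procedure that, on its natural reading, breaks it. The Intervention sentence ties supervision to one session in the clinic and assigns training separately to the nurse, so attendance is what most site staff would infer. If physician and nurse both supervise, the physician is present and the conflict is sharper. Withholding the assignment list does not help when the assignment can be read from the leg.

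**Conclusion.** The concern holds and should be fixed. Three things are certain from the text: the two accounts of the first session name different supervisors, electrode site identifies the arm, and the Visit 3 rater is not identified. The conflict with the blinding rule is by implication: it arises if the supervising physician sees the electrodes. Loss of blinding in an outcome further requires that this physician is also the rater.

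If those conditions are met, the physician-rated global response, one of four numbered secondary outcomes, cannot be described as blind-rated, and nothing planned would detect it. The primary comparison, the sample size and the other secondary measures are not directly affected.

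**What to change.** 1. Reconcile the Intervention section with Appendix 2 on who attends the first session, so that the Study design rule holds. The Appendix 2 wording already agrees with that rule. If supervision in the Intervention section means overall responsibility only, say so, and state that this physician does not see electrode placement.
2. Add to item 4 of the secondary outcome measures: *The assessment is made by a physician who has not seen this patient's electrode placement or device use.*
3. As a modest extra, add that the rater does not ask about electrode location when taking the history, and that the study nurse asks the patient beforehand not to describe it. This closes a separate route, since patients treat themselves at home and know where the electrodes go.

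The cost is a wording change in two places and, with step 3, one reminder at Visit 3. No extra visits, data or staff are needed if the first session follows Appendix 2. If a physician is to attend and see the electrodes, a different physician must rate at Visit 3, and the sentence limiting knowledge to the nurse must be amended.

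### Eight secondary measures have a pre-treatment value that the planned t-test does not adjust for; ANCOVA would usually be more precise at no extra data cost

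*Combined protocol and SAP*

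**What the plan says.** The section Data Analysis and Sample Size gives one sentence to the secondary outcomes: "Secondary endpoints will be analyzed as appropriate using the students t-test or chi squared test". No covariate, ANCOVA or regression model appears anywhere in the document. The quantity to be tested is also left open. By contrast, the primary outcome is explicitly a change, with response defined as "score improvement by 2 points between screening visit 1 and end of study visit 3".

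The Appendix 2 schedule shows which secondary measures have a pre-treatment value:

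- **OAB-q SF:** completed at Visit 1 and Visit 3.
- **Voiding diary:** issued at Visit 1; at Visit 2 the entry reads "Completed diary returned & new one provided for Visit 3". The Secondary outcome measures section lists six parameters from it.
- **24-hour pad test:** supplies issued at Visit 1; at Visit 2 the entry reads "Pads Returned & new ones provided for Visit 3".

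That makes 1 + 6 + 1 = 8 measures with a value on each side of treatment. The physician assessment of benefit is made at Visit 3 only and has no baseline.

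**The concern.** Whichever t-test is meant, information already collected is lost. A comparison of Visit 3 values leaves all between-patient variation in the error term. A comparison of changes subtracts the whole baseline, which adds baseline noise when r is modest. ANCOVA estimates how much of the baseline to remove.

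The stake is precision on the trial's quality-of-life, diary and pad-weight results, for which the plan states no power. A second, smaller stake is that the analysed quantity is not fixed in advance. Either t-test is valid if chosen beforehand. In a null simulation (40,000 runs, normal data, 27 per arm), reporting the smaller p-value of the two gave 8.8–9.2% false positives for r between 0.3 and 0.7. Nothing suggests that this is intended, but naming one analysis rules it out.

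Pad weight and urgency-incontinence episodes need separate thought. Entry requires "Failure of behavioral measures and pharmacologic therapy to adequately control overactive bladder symptoms" but does not require incontinence, so these two measures may be skewed with many zeros. The share of dry patients is unknown.

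**Working it through.** **The plan's own figure.** The only sample size is for the primary responder outcome: 20% against 60%, two-sided alpha 0.05, 80% power, 27 per group. The normal-approximation formula gives 23 without and 28 with continuity correction. Exact power at 27 per group is 80.2% for the continuity-corrected chi-squared test (86.8% uncorrected), so 27 is reproduced. With 10% dropout, 27 / 0.9 = 30 per group, 60 in total. The checks below use n = 27 per arm.

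**Variance of the treatment difference**, relative to a t-test on final values, with equal SDs at both times and baseline-to-final correlation r:

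- final value: 1
- change: 2(1 − r)
- ANCOVA: (1 − r²) × [1 + 1/(2n − 4)] = (1 − r²) × 1.02. The factor 1 + 1/50 is the cost of estimating the slope.

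Example at r = 0.5: change = 2 × 0.5 = 1.00; ANCOVA = 0.75 × 1.02 = 0.765.

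The documents do not give r, so a range is assumed. Power and detectable difference come from the noncentral t distribution (52 df for the t-tests, 51 for ANCOVA). The 0.6 SD effect is also an assumption.

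| | r = 0.3 | r = 0.5 | r = 0.7 |
|---|---|---|---|
| ANCOVA variance / final-value variance | 0.93 | 0.77 | 0.52 |
| ANCOVA variance / change variance | 0.66 | 0.77 | 0.87 |
| Difference detectable with 80% power (SD): final | 0.78 | 0.78 | 0.78 |
| – change | 0.92 | 0.78 | 0.60 |
| – ANCOVA | 0.75 | 0.68 | 0.56 |
| Power for 0.6 SD: final | 58% | 58% | 58% |
| – change | 45% | 58% | 80% |
| – ANCOVA | 61% | 70% | 85% |

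Without the slope cost the variance ratios are 91%, 75% and 51% against final values, and 65%, 75% and 85% against change.

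At r = 0.5 a final-value t-test would need 27 / 0.765 ≈ 35 per arm to match ANCOVA's variance.

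**Break-even points.** Against final values: (1 − r²) × 1.02 = 1 gives r² = 0.0196, r = 0.14. Against change: 1.02(1 + r)/2 = 1 gives r = 0.96. Below r = 0.14 ANCOVA loses slightly to the final-value test; at r = 0 power for 0.6 SD is 57% against 58%.

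**Simulation check** (normal data, r = 0.5, 0.6 SD, 20,000 runs): final 58.1%, change 58.1%, ANCOVA 69.5%. ANCOVA type I error was 4.9–5.0%.

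**Pad weight**, where normality is doubtful. Assumed model: zero-heavy log-normal, median 20 g, log SD 1, r = 0.6, 10,000 runs per scenario. Wet/dry switching is equal in both arms, with prevalence held constant. Power when 0 / 10 / 20% of wet patients become dry:

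| | change t-test | final t-test | raw-scale ANCOVA |
|---|---|---|---|
| One third wet, 50% reduction | 14 / 13 / 11% | 10 / 11 / 10% | 19 / 16 / 14% |
| 60% wet, 65% reduction | 40 / 34 / 29% | 47 / 47 / 47% | 69 / 61 / 56% |

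Raw-scale ANCOVA was ahead of both t-tests in all 12 non-null scenarios run with one third or 60% wet. Its type I error was 3.6–4.1% (t-tests 3.2–4.2%). In the second row, ANCOVA on log(1+x) gave 92 / 49 / 34%, so its advantage depends on patients not moving between wet and dry. Urgency-incontinence episodes were not simulated.

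**The case against.** The planned tests are valid under randomization, the trial is sized only on the primary responder rate, and no power is claimed for any secondary endpoint. This is therefore an efficiency choice and not an error. That stands and sets the weight of the point. The ambiguity over final value or change could be cured in one sentence without ANCOVA; that is also true, but it would leave the precision unused.

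The primary outcome is a change, so a reader might expect t-tests on change for the rest. The plan also describes the diary and pad test as reliable, which might suggest a high r. ANCOVA then adds less: 80% to 85% at r = 0.7 and 93% to 95% at r = 0.8 for 0.6 SD. This is fair, but the text does not say change, and ANCOVA still does no worse unless r exceeds 0.96.

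The gain is conditional on r. Below about 0.14 there is none over a final-value test. This stands; the possible loss is about 2% in variance.

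For pad weight, the ranking of raw-scale over log ANCOVA rests on the assumed log SD of 1. At log SD 1.5 with 20% switching, log ANCOVA was ahead: 24% against 18% (60% wet, 65% reduction, r = 0.3), and 9% against 6% (one third wet, 50% reduction, r = 0.6). So the choice between the two scales is not settled. Raw-scale ANCOVA still matched or beat both t-tests in every scenario examined.

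Two points of wording also stand. ANCOVA needs the pre-treatment value, so a missing one must be dealt with. And the OAB-q SF is described as covering both symptom bother and quality of life; if these are scored separately there are nine measures and not eight.

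**Conclusion.** The concern holds. Eight secondary measures have a pre-treatment value, and the plan neither adjusts for it nor says what the t-test compares. Over r from 0.3 to 0.7 at 27 per arm, ANCOVA has 52–93% of the variance of a final-value t-test and 66–87% of that of a change-score t-test. For an assumed 0.6 SD effect it adds 3 to 27 points of power over the first and 5 to 16 over the second. The size rests on an assumed r and, for most measures, on approximate normality. The pad-weight figures rest on a fully assumed distribution and support only the direction. The loss is of precision: type I error of a test fixed in advance, the primary analysis and the total of 60 are untouched. The change is worth making because it is nearly free.

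**What to change.** Replace the secondary-endpoint sentence with wording such as:

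> Each continuous secondary endpoint with a pre-treatment value (OAB-q SF, the six diary parameters, 24-hour pad weight) will be analysed by ANCOVA of the Visit 3 value on treatment group with its pre-treatment value as covariate, reporting the adjusted difference with 95% CI. For pad weight and urgency-incontinence episodes, ANCOVA on log(1+x) is a sensitivity analysis only.

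The physician assessment has no baseline and stays unadjusted. When this is written in, also name the OAB-q SF score or scores to be analysed, and state how a patient with a Visit 3 value but no pre-treatment value is handled, so that nobody is dropped by default.

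The cost is two sentences of text plus those clarifications and a few lines of SAS, with no new data, visits or patients. The downside is up to about 2% in variance against a final-value t-test if baseline and final values are nearly uncorrelated. If few patients are wet, pad weight remains weakly powered under any of these methods.
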